## **Data and Safety Monitoring Plan**

The Data Safety and Monitoring Plan includes data monitoring, the monitoring and analysis of adverse events, and the description of adverse events; it is presented in accordance with the Interim Guidelines for Reporting Adverse Events to NIH IRBs (<http://ohsr.od.nih.gov/info/>) and NIH Policy for Data and Safety Monitoring (<http://grants.nih.gov/grants/notice-files/not98-084.html>). The PIs will report to RP's IRB (Tanglewood), our DSMB, and NIH/NIAAA. The guidance for reporting adverse events will be followed for any adverse events; for serious adverse events, reporting will include the verbal reporting of the event within 24 hours and providing a written report of the event within 72 hours. Expected, non-serious adverse events will be reported at the time of annual, continuing IRB review of the study.

### **Potential adverse events resulting from participation:**

- Distress answering questions
- Discomfort participating in study activities
- Breach of confidentiality
- Disclosure of crime (i.e. substance use) committed by adolescent
- Iatrogenic effects of the PN curriculum

### **Risk management protocols in place to deal with adverse events.**

All project staff will be trained to recognize adverse events at quarterly training sessions that all staff must attend. Opportunities to report events will occur during monthly staff meetings and as they arise.

Parents of students will be required to sign a parental consent form prior to any involvement by the youth in any phase of the study. The consent will acknowledge the potential for events described above. Students will provide assent prior to participation. Parent consent and youth assent to research activities will be obtained through an online process. Only by agreeing to these procedures can the student access the study.

All team members will follow all IRB, RP, and university guidelines that pertain to the handling the identity of human subjects. Informed consent/assent documents will be kept in a locked cabinet in the PI's ([name]) office.

### **Plan for Data Monitoring**

**Confidentiality and Data Security.** De-identified data will be maintained in a study-specific database on [name] computer. Customized data management protocols will be developed to confirm the validity and consistency of the data. Confidentiality will be maintained by storing subject names and associated study identification numbers in a separate computerized file maintained on a CD and stored in a locked file cabinet at GfK. Study data will be accessible only through a password-accessible account, which will be maintained by the GfK supervisor.

All data and other information in this study will be maintained confidentially but will not be anonymous due to the longitudinal nature of participation. To protect against risks posed by a potential loss of confidentiality, we will take the following steps: First, subjects will be assured that they are free to refrain from answering any questions they do not wish to answer. Second, all data will be identified only by a unique personal identifier (PIN), which will be randomly generated for study purposes. Web-based data will be collected using a secure server supporting 128-bit encryption. This level of encryption provides the highest level of protection against hackers, computer break-ins, etc. GfK, with extensive experience with sensitive data collection, have secure servers and will sign a confidentiality agreement. A master list of

names and code numbers will be stored in locked file cabinets under the supervision of the GfK supervisor and will be available only to research staff on this project. Experienced research assistants will be employed. Research assistants will receive training that includes emphasis upon the importance of confidentiality of information, and all personnel on the project will complete the required NIH training in protection of human research participants. All staff will sign confidentiality statements. Data will be retained on computers with restricted and password protected access, without links to the master code list. All data based on this research will be reported in aggregate form. No individual respondents will be identified. Finally, using new NIH policy, we will be automatically granted a Federal Certificate of Confidentiality to address our proposed research. This certificate offers the highest protection available by law for research data. We have previously used these certificates in our work with college student and adolescent drinkers.

All project staff will be required to complete and be current with certifications on the NIDA Clinical Trials Network six-hour training on good clinical practices. The current training includes modules on: IRBs, informed consent, confidentiality and privacy, participant safety and adverse events, quality assurance, the research protocol, documentation and record keeping, research misconduct, roles and responsibilities, recruitment and retention, and investigational new drugs.

### **Plan for Monitoring and Reporting Adverse Events**

As described in the human subjects section, all participants are encouraged to contact project staff to report complaints or adverse events and will be given a telephone number and email address. Instructions for reporting adverse events and complaints, as well as for contacting the investigators, are included in the consent documents and on all contact information provided to participants through the course of the study. [name] has conducted research for over 30 years in the area of risky substance use prevention and is highly experienced in dealing with these types of issues. [name] and [name] have similar experience, are competent to handle any adverse events that may arise.

Our measures do not assess individuals at risk of immediately harming themselves (e.g., suicidal ideation); therefore, we will not have to screen the data to potentially intervene with individuals who may be a risk to themselves.

Members of the research team have conducted federally funded research on populations of children and adults over the past 30 years and are competent to handle any adverse events that may arise. The research team has conducted and/or had primary leadership roles on several grant funded clinical studies. Both are experienced and qualified to distinguish serious adverse events.

We will notify the RP IRB, our project officers, and NIH (e.g., NIAAA) within 24-48 hours of any serious adverse event. We will provide an annual report to the NIH (e.g., NIAAA) Project Officer summarizing all adverse events should any arise.

## Section 4 - Protocol Synopsis (Study 1)

### 4.1. Brief Summary

High school students' alcohol, nicotine, and marijuana use are major public health problems. Among the many consequences of these risky behaviors are impaired driving and impaired passenger fatalities as well as increased health risks. Both school administrators and parents have requested parent-based interventions (PBIs) for the general high school population that include content on alcohol, nicotine and marijuana use. In addition, digital materials are needed for the "on-the-go" parent. The proposed research will address this omission, curb the alarming trends noted above, and move the field forward by conducting a randomized controlled trial testing a modified, digital version of the Parent Handbook for the all high school students that includes additional content for parents to have broader discussions about combined alcohol nicotine and marijuana use alone (referred to as Parenting Now).

### 4.2. Study Design

#### 4.2.a. Narrative Study Description

High school students' alcohol, nicotine and marijuana use are major public health problems. Among the many consequences of these risky behaviors are impaired driving and impaired passenger fatalities plus elevated health risks. These concerns are further magnified by reports about alcohol showing: 1) younger drivers are overrepresented in fatal crashes involving impaired drivers; 2) nearly 1 in 5 nighttime weekend drivers are under the influence of combined alcohol and marijuana or marijuana alone; and 3) although over 1.3 million drivers in the U.S. are arrested for impaired driving annually, they only represent 1% of the estimated 121 million self-reported episodes of impaired driving each year. Despite the evidence that our prior brief parent-based interventions (Parent Handbook) for college students have reduced risky drinking and are currently being used on many campuses, there are no digital PBIs with specific content for reducing combined alcohol, nicotine and marijuana in the general high school student population. The proposed research will attempt to address this omission, curb the alarming trends noted above, and move the field forward by conducting a randomized controlled trial testing a modified version of our PBI that includes content for parents to have broader discussions about alcohol and marijuana (referred to as Parenting Now). The study will use an extremely rigorous design that meets the Society for Prevention Research Criteria for Efficacy, a nationally representative sample to significantly increase its generalizability, and an examination of gender differences. To the extent that the research is successful, it will provide an easy to implement and low-cost alternative that can be widely disseminated to address this important public health problem. For example, D.A.R.E. has agreed to implement Parenting Now as part of its high school curriculum.

Parenting Now will be refined and completed based on our successful Phase I research that identified the need for core and optional modules. The core provide a common base of information. The optional modules allow content to be customized, a feature of engaging and effective digital health promotion. In addition, we will personalize content based on parents

styles of communication about substances. This will produce an efficient, engaging and effective means to enhance parents' ability to reduce prevalence of alcohol use and consequences, and other substance use.

The design is a two-arm randomized control trial with 3 waves of data collection (Parenting Now v active control). The study will enroll a nationally representative sample of 400 parent-student dyads through GfK Custom Research (formerly known as Knowledge Networks). All dyads will complete assessments of all the variables at three times: pre-intervention baseline, immediate follow-up (1mo.), and follow-up posttest(6-mo.). The sample will be drawn from the GfK KnowledgePanel that closely approximate U.S. census figures (exclusion criterion will lead to under-representation of monolingual Hispanics whose inclusion would make the study cost prohibitive).

#### 4.2.b. Primary Purpose

Prevention

#### 4.2.c. Interventions

Type	Name	Description
Behavioral (e.g., Psychotherapy, Lifestyle Counseling)	Parenting Now Intervention that includes content on alcohol, nicotine, and marijuana	Preventive Parenting Now digital intervention emphasizing parent-teen/young adult communication on drinking/risks of drinking/risks of alcohol abuse, with the addition of a communication component on the risks of nicotine and marijuana use, with the goal of reducing alcohol, nicotine and marijuana use in college students

#### 4.2.d. Study Phase

Early Phase 1 (or Phase 0)

Is this an NIH-defined Phase III Clinical Trial?

Yes

No

4.2.e. Intervention Model

Other

Two-arm randomized trial

4.2.f. Masking

Yes

No

Participant

Care Provider

Investigator

Outcomes Assessor

4.2.g. Allocation

Randomized

4.3. Outcome Measures

Type	Name	Time Frame	Brief Description
Primary	Alcohol Use	Project years 1-2	A standard drink definition will be provided: a standard drink consists of 12 oz. beer or wine cooler, 8.5 oz. of malt liquor, 4 oz. of wine, 3.5 oz. fortified wine, or 1.5 oz. of hard liquor. Typical weekly drinking: participants will respond to the Daily Drinking Questionnaire(DDQ; Collins et al., 1985) to indicate number of drinks consumed on each day of a typical week within the past six months. Participants will report maximum number of drinks consumed on an occasion within the past month and number of hours spent drinking on that occasion using the Quantity/Frequency/Peak questionnaire (QFP; Dimeff et al., 1999; Marlatt et al., 1998). Drunkenness will be assessed by asking how many times in the past month participants have gotten drunk, or very high from alcohol using a 6-point scale: (0) never to (5) 9 or more. Heavy episodic drinking will be measured for females and males separately, asking for number of times they've had 4/5, respectively, drinks in a row within two hours.
Secondary	Marijuana Use	Project years 1-2	Frequency of use will be assessed by asking how often participants used marijuana during the past six months using a 7-point scale ranging from (0) never to (6) 40 or more times.
Secondary	Combined Use	Project years 1-2	Frequency of combined use will be assessed for participants indicating marijuana and nicotine use with a single item: During times you used marijuana, how often did you also drink alcohol? using a 6-point scale ranging from (0) never to (5) 40 or more times. For participants that indicate their peak drinking occasion a follow up question will assess whether marijuana or nicotine was also used(yes or no).
Secondary	Consequences of Alcohol Use	Project years 1-3	Alcohol-related consequences (e.g., said or done embarrassing things, blackout) from the past six months will be measured using the established Brief Young Adult Alcohol Consequences Questionnaire (BYAACQ; Read, Kahler, Strong, & Colder, 2006). Response options will again be measured on the same a 7-point scale above.
Secondary	Nicotine Use	Project years 1-2	Frequency of use will be assessed by asking how often participants used nicotine products (tobacco, vaping, snuff) during the past six months using a 7-point scale ranging from (0) never to (6) 40 or more times.

Other	Alcohol Motives (tertiary/other outcome)	Project years 1-2	Using the past six months as a time reference, participants will be asked about their motivations to use alcohol. Twenty items for each substance will assess motives for using alcohol, such as ?to be sociable? and ?to forget about your problems? on a 5-point scale ranging from (1) almost never/never to (5) almost always/always.
Other	Alcohol Expectancies (tertiary/other outcome)	Project years 1-2	Alcohol expectancies will be measured using a 7-point scale ranging from (-3) strongly disagree to (3) strongly agree. Items will assess how likely a variety of alcohol-related consequences will be experienced in the next few months. For example, items, be worded specifically for alcohol use, such as ?I will feel badly about myself because of my drinking.?
Other	Alcohol Willingness (tertiary/other outcome)	Project years 1-2	Response options for willingness items will be on a 7-point scale ranging from (1) strongly disagree to (7) strongly agree. Willingness to use alcohol will be measured to assess participants? willingness to 1) drink once or twice in two hours; 2) drink 3-4 times in two hours; and 3) drink 5+ times in two hours. Willingness to use marijuana and COMBINE will be assessed individually with four items asking their willingness to use marijuana/ COMBINE occasionally, regularly, weekly, and daily.
Other	Alcohol Norms (tertiary/other outcome)	Project years 1-2	Perceived norms of drinking for the past six months will be measured using the DDQ using closest friend as a referent. To assess peer injunctive norms of alcohol use participants will be asked to indicate how acceptable their closest friends would find of a list of situations (e.g., drinking enough alcohol to pass out) using a (1) strongly disapprove to (7) strongly approve scale.
Other	Parental Communication (other/tertiary outcome)	Project years 1-2	Parental communication about alcohol, nicotine, and marijuana use, COMBINE, and alcohol consequences will be assessed separately for parent and teen. Participants will be asked whether their parent discussed these topics (yes/no) with them within the past six months. Items include topics such as ?the importance of not being pressured to drink to fit it? and ?how marijuana works in the body?.

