**Table 2. Measures Reflective of Theoretical Model in Figure 1**

Construct	Target	Time	alpha
Primary Outcomes			
Alcohol Use (Daily Drinking, HED, Quantity/Frequency, Peak) 	Teen	T1-T3	>.70-.90
Alcohol-related Consequences (e.g., Riding with a drunk driver) 	Teen	T1-T3	>.75-.85
Secondary Outcomes			
Marijuana Use 	Teen	T1-T3	>.70-.90
Nicotine Use (e.g., Cigarette Use; E-cigarette Use; Smokeless Tobacco) 	Teen	T1-T3	>.70-.90
Combined Substance Use	Teen	T1-T3	>.70
Tertiary Outcomes (Mediators)			
Parent Communication 	Parent,Teen	T2	>.75
Alcohol Motives/Expectancies/Willingness/Norms 	Teen	T2	>.70 - >.85
Moderators			
Background Demographics (Birth Sex, Gender Identity, Sexual Orientation, Age, Race / Ethnicity)	Teen	T1	–

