### **Specific issues and approaches for the analyses of the Specific Aims.**

**Aim 1: Evaluate the efficacy of PN intervention.** The primary focus of the analyses will document differences on our primary outcomes (alcohol use and alcohol-related harms) and secondary outcomes (marijuana use, nicotine use, and their combined use with alcohol) between the groups (PN/Control) using a mixed measures analysis of variance. A 2 X 3 (groups X time) MANCOVA will test the impact of the PN intervention on our outcome variables contrasting baseline tendencies against follow-up assessments (3 waves: baseline, 1 mo., and 6 mo.). For Aim 1 (analysis of efficacy), we will conduct an intent-to-treat analysis that will include all individuals who have been randomized to a condition. We will also examine differences in all outcomes by sex of the student (as a relevant biological variable), sexual orientation, and gender identity adding these as covariates to the analyses. We will be sensitive to inflated experiment-wise error rates and control these with modified Bonferroni methods.

**Aim 2: Examine mediators.** The second aim examines mediation paths in Figure 1 using SEM. We will follow the recommendations of MacKinnon (joint significance). For example, we will examine the relationship between the effects of the PN on predictors at the immediate post-PN assessment (1 mo. follow-up) and their subsequent effects on outcomes at the 6 month follow-up. The models will be statistically over-identified. We will examine global fit indices and focused indices of fit diagnostic of specific points of ill fit in the model (e.g., standardized residuals for predicted minus observed variances and covariances, and modification indices). We will use robust standard errors and bootstrapping. In the face of poor model fit, we will examine diagnostics that are conceptually meaningful and will significantly improve model fit.

[figure not shown]

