### **Multiple Trajectories that Covary.**

The analyses can be extended to identify multiple trajectories that covary over time and by group (PN/Controls; Figure 3). For example, the analytic approach would examine the changes over time in parental communication (PCOM) associated with the changes over time in alcohol use and include the effects of time-invariant covariate of PN (vs. controls). This growth curve can be expanded to include other constructs (e.g., parent communication). The focus is on trajectories of change over time rather than single variables. These analyses have not been done in any previous research examining brief PN efficacy or mediation processes in alcohol use but have been used

in other risky behavioral areas with good effect. This also can be modified for lagged effects and complex structural dynamics typically discussed in traditional panel analysis. It is possible to parameterize a growth curve model in traditional panel analysis terms like it is possible to parameterize traditional panel analysis in growth curve model terms. The mathematical details can be rather complex, and our experience is that typical social science readers are more comfortable with one framework or the other, depending on the research question. Our point is that for questions that pursue the analysis of the relationship between multiple trajectories, fairly complex causal dynamics and error structures can be modeled.

**Limitations/Alternative Strategies for Aim 2.** An alternative would be to recruit a school district or an adequate number of schools, randomly assigning schools to condition. This would not, however, produce a nationwide sample and would be costly in recruitment and tracking. Administration under these conditions is not, however, directly analogous to eventual dissemination. We accept this tradeoff for the advantages of a representative, national sample.

**Indicators of Success/Benchmarks.** One indicator of success will be if we hit initial, 1- and 6-month recruitment and retention targets. Secondly, we expect a high degree of fidelity (i.e., 80% accessing all required material and at least one optional section). The next indicator would be short term effects on mediators on the 1-month follow up. Finally, and most importantly, will be significant effects on behavioral outcomes with a successful test of the conceptual model in Figure 1.

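### At the 1-month wave the yes/no parent-communication items look back six months, so talk from before the intervention scores yes and shrinks the T2 contrast

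*Combined protocol and SAP*

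**What the plan says.** **Windows.** Section 4.3 (Outcome Measures) assesses communication separately for parent and teen: "Participants will be asked whether their parent discussed these topics (yes/no) with them within the past six months". Six other measures have the same look-back:
- weekly drinking ("to indicate number of drinks consumed on each day of a typical week within the past six months")
- consequences ("from the past six months will be measured using the established Brief Young Adult Alcohol Consequences Questionnaire")
- motives ("Using the past six months as a time reference, participants will be asked about their motivations to use alcohol")
- descriptive norms ("Perceived norms of drinking for the past six months will be measured using the DDQ using closest friend as a referent")
- marijuana use
- nicotine use

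Peak drinks and drunkenness use the past month. Expectancies look forward. No section states a different window for any wave.

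**Timing of T2.** Participant Recruitment and Procedures puts it one month after baseline. Data Collection and Measurement puts it one month after the intervention. Parents in both arms are told to talk with their teens in the month after receiving the link.

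**Use of T2.** H4 predicts more discussion by PN parents than by controls. The Aim 2 analysis takes PN's effect on the mediators at 1 month and relates it to outcomes at 6 months. The Benchmarks paragraph adds: "The next indicator would be short term effects on mediators on the 1-month follow up".

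**Waves for the mediators.** Table 2 lists Parent Communication and "Alcohol Motives/Expectancies/Willingness/Norms" at T2 only. Randomized Trial Design says youth report all Figure 1 variables at three times; 4.2.a and Statistical Design and Power say the same of dyads. Protection of Human Subjects lists motives, norms and parenting behaviors at baseline. Table 1 surveys parents at T2 only.

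**The concern.** A yes/no item over six months cannot separate a conversation prompted by PN from one held three months before enrolment. A dyad that had already covered a topic scores yes in either arm, whatever PN does, so only dyads that had not yet talked can show a difference.

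Three parts of the plan rest on that difference at T2: the 1-month reading of H4, the first link of the Aim 2 mediation path, and the 1-month mediator benchmark. A null result there could mean that PN did not change communication, or that the item mostly recorded the period before PN. The data would not tell these apart, and the wording cannot be changed after collection.

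**Working it through.** **1. The plan's own figure.** Statistical Design and Power claims power above 0.80 for an effect of 5% of outcome variance with about 200 per arm. Alpha is not stated; I take two-sided 0.05.
- f² = 0.05/0.95 = 0.0526, so d = 2√0.0526 = 0.459.
- Noncentral F with 1 numerator df: 0.996 at N = 400; 0.983 at the 320 dyads expected at 1 month; 0.969 at the 280 expected at 6 months (Participant retention).

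The claim is reproduced for a contrast that is not diluted.

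**2. Share of the window before the intervention.** With one month of exposure at T2, (6 − 1)/6 = 83%. With three weeks it is (6 − 0.75)/6 = 87.5%, and with two weeks 91.7%. Both stated anchors for T2 give at least five sixths. Late log-on raises it, and the plan allows three weeks of reminders before telephoning.

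**3. Yes/no item.** Let q be the share of dyads who had already discussed the topic in the earlier months, and p the share who discuss it in the month after the link. Then

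P(yes over six months) = 1 − (1 − q)(1 − p),

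so the difference between arms is (1 − q) times the one-month difference. This takes earlier and later talk as independent. In general the factor (1 − q) applies to the one-month difference among dyads that had not yet talked.

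Assumed for illustration: p = 0.40 in control and 0.60 in PN. From the plan: 320 dyads, so n = 160 per arm.

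Power = Φ{[Δ − 1.96√(2p̄(1 − p̄)/n)] / √([p₁(1 − p₁) + p₀(1 − p₀)]/n)}.

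For q = 0.4: Δ = 0.76 − 0.64 = 0.12, p̄ = 0.70, and (0.12 − 1.96 × 0.0512)/0.0508 = 0.386, giving 0.65.

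| Already talked (q) | Control | PN | Difference | Power |
|---|---|---|---|---|
| 0 | 0.40 | 0.60 | 0.20 | 0.95 |
| 0.4 | 0.64 | 0.76 | 0.12 | 0.65 |
| 0.6 | 0.76 | 0.84 | 0.08 | 0.43 |
| 0.8 | 0.88 | 0.92 | 0.04 | 0.22 |

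**4. What a baseline report can recover.** Suppose the teen's baseline answer identifies earlier talkers without error and covers exactly the earlier part of the T2 window. The comparison can then be made among the dyads that had not talked, at 0.40 against 0.60, with n = 160(1 − q) = 96, 64 or 32 per arm. The same formula gives 0.80, 0.62 and 0.36. This is a best case: recall error lowers it, and parents have no baseline survey in Table 1.

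**5. The other six measures.** If a fraction k of d = 0.459 survives at T2, power at 160 per arm (normal approximation) is 0.10 for k = 1/6, 0.28 for k = 1/3, 0.54 for k = 1/2 and 0.98 for k = 1. Nothing in the documents fixes k.

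**6. The 6-month wave.** At T3 the six-month window falls almost wholly after the intervention, so items asked there have a clean window.

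**The case against.** **T3 may rescue H4.** H4 names no time point. If the three-wave text is followed instead of Table 2, teen communication is reported again at T3 over a post-intervention window. This stands for the teen report. It does not help the mediation path, which takes its mediator at T2, or the 1-month benchmark, or the parent report in Table 1.

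**Share of time is not loss of effect.** A reader might infer that five sixths of the effect is lost on all seven measures. The documents do not support that. A typical-week answer, a motive rating and a perception of a friend's drinking need not average six months evenly, and a perception can change even when it refers to an earlier period. This stands, and it limits the quantified claim to the communication items.

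**A constant window suits the 2 × 3 group-by-time model.** That is a fair reason to keep the six-month wording for the use and consequence items. Moving them to 30 days has its own cost. At the 22.7% past-30-day use quoted for ages 16–17, 0.227 × 320 ≈ 73 teens, about 36 per arm, would report drinking. If only they carry the 5% effect, power is about 0.48.

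**Other evidence on talk.** Fidelity of PN Use has parents rate discussion of PN topics on 4-point scales. No recall window is stated for it, and it is not the Section 4.3 outcome.

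**The survey is not in the documents.** Section 4.3 holds brief descriptions, and Appendix B may word the items by wave. This stands and cannot be settled here.

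**Conclusion.** The point holds for the communication items at T2. As written, they count pre-intervention talk, and the contrast shrinks by the share of dyads who had already talked. That share is not in the documents, so the fall from 0.95 to 0.65, 0.43 or 0.22 is an illustration. It rests on a single item, one-month rates of 40% and 60%, independent earlier and later talk, and 160 per arm. Baseline adjustment recovers part of the loss for teens, if communication is in fact collected at baseline.

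For motives, descriptive norms, weekly drinking, consequences, marijuana and nicotine the same mismatch exists at T2, but its size cannot be estimated. The 6-month contrast is largely unaffected.

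A reader might also take the Year 1 timeline (pretest month 6, treatment month 9, posttest month 10) to mean a gap of several months between baseline and T2. It places the pretest before recruitment in month 7, so it cannot carry that inference.

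The change is worth making before data collection. Confidence is medium because the questionnaire is not available.

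**What to change.** 1. At T2, word the communication items as *since the link was sent* or *past 30 days*, for parent and teen, with a matching 30-day version for teens at baseline. Use this version for the 1-month test of H4 and for the T2 mediator.
2. Reconcile Tables 1 and 2 with Randomized Trial Design, 4.2.a, Statistical Design and Power and Protection of Human Subjects, so that teen communication, motives and norms are collected at T1 and T3 and the T2 models adjust for baseline.
3. Keep the six-month wording for the 6-month contrast. For alcohol use at T2, rely on the past-month items already planned (peak drinks, drunkenness), and label the six-month use and consequence items at that wave as supportive.
4. If Appendix B already uses wave-specific windows, correct Section 4.3 to say so; step 2 is still needed.

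The cost is a few duplicated yes/no items in surveys of 25–30 minutes. Converting the use, consequence and motive items to 30 days is a separate trade-off because of the extra zeros, and is not part of this minimum.
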